To evaluate the safety and acceptability of the ShangRing for device-based circumcision in routine clinical settings, as a part of a comprehensive HIV prevention program for males aged 13 and older in Tanzania.

Evaluation Objectives

The specific objectives of the proposed implementation pilot is to:

- Describe/assess the safety of the ShangRing device by the occurrence of clinical adverse events (calculated as a rate), when circumcision is performed by trained mid-level providers;
- Ascertain capacity and required clinical capabilities of clinical staff of various cadres to carry out ShangRing procedures;
- Describe/assess male client and provider acceptability of the ShangRing device and process (e.g. need to return to the clinic for device removal, tolerance for leaving device in situ);
- Assess the percentage of clients clinically healed 6 weeks (42 days) following the removal of the device;
- Determine the time at which point all clients are physically healed following the removal of the device.

Primary Endpoint

The primary endpoint related to the goal and objectives of the evaluation is to:

- Measure the incidence of mild, moderate and severe AEs associated with ShangRing procedures including both procedure and post-procedure events, and all device-related malfunctions such as early spontaneous displacement. The primary endpoint will be assessed at device placement, at device removal, 3-days post removal, at the day 49 post-placement healing assessment, and at any unscheduled visit in that time frame. Adverse events will be measured and described in the following ways:
 - Total numbers and types of known AEs occurring among clients, including all severities of AEs (mild, moderate, severe) and serious AEs (see below), including detailed information about all instances of device displacement/detachment/self-removal/malfunction, need for medical attention or intervention, and final outcomes in those experiencing AEs.
 - Total number of clients with known AEs (may be different from above if clients experience multiple AEs), including all severities of AEs and serious AEs.

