Males who present with exclusion criteria for one of the medical reasons listed above will be referred to the appropriate specialist for management of their conditions. Additionally, any men who have an anatomic contraindication but still want circumcision, can be referred to an urologist for further management. In keeping with standard national practice, clients presenting with specific disease conditions such as STIs or TB may be treated on-site or referred for care elsewhere if appropriate services are not available on site. Furthermore, males who are HIV+ will be assessed to determine if they are on antiretroviral therapy (ART). Those not on ART will be referred for ART.

Client Withdrawal Criteria

A client has the right to withdraw from the evaluation at any time, for any reason, without prejudice to his future medical care by the provider or the health facility (see Appendices V and VI for the client and minor client assent forms). If a client withdraws after consent, but prior to device placement, the client will be replaced until the desired sample size is reached and the data will be excluded from analysis. If a client withdraws after device placement, the client will not be replaced and the existing data will be included in the analysis, but no attempts will be made to collect further data other than that required for clinical documentation of the removal visit. The reason, timing and circumstances of the withdrawal will be documented and analyzed. The client will subsequently not be included among those selected for the day 28 in-person interview, nor will they be asked to return for the day 49 follow-up visit to assess healing. When the client withdraws, they will be informed that they may still return to the clinic for removal of the device as scheduled, and contact the clinic should they have further questions, suffer an AE, or experience other difficulties healing.

A client will be informed in advance that if he wishes to withdraw from the evaluation after ShangRing placement but before scheduled removal, he must still return to the provider for device removal on day 7 for his own health. The client will also be advised that once applied, it is not safe to remove the device before day 5. If the client requests removal on day 5 or 6, it will be removed as requested. The number and reasons for client withdrawals will be recorded and included in the final evaluation report (See Appendix XXII).

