Procedure for Handling Clients Lost-to-Follow-Up

Clients who are lost to follow-up after device placement, and therefore do not return to have the device removed, will not be recorded as experiencing an AE, and also will not be included in calculations when measuring AEs.

In the event that a client refuses to return for follow-up, ShangRing has been shown to detach on its own. Studies show that for those clients who do not come in to have the device removed, and wear it for more than

seven days, the ShangRing will eventually spontaneously detach on its own, and healing will progress normally. In one study, complete detachment of the device occurred in 66.7% of men who wore the device for more than seven days, and 14% of men requested removal of a partially detached device 8-14 days after placement. No severe or serious AEs were reported among this group.²⁹

A study of delayed removal of ShangRing in Kenya found that in 81.8% of men the ShangRing had completely detached on its own between 10-16 days after circumcision.³⁰ By 21 days following the circumcision the ring had at least partially detached in 100% of men, and was completely detached in 93.7%. While the ShangRing has been found to be safe if left on, this is not the recommended standard of care for the purposes of this evaluation, and clients will be followed up with for device removal as described in this protocol.

Provider Participant Inclusion Criteria

Providers meeting the following criteria will be included in the evaluation:

- Adult aged 18 or older
- Employed as a medical doctor, Assistant Medical Officer, Clinical Officer, professional nurse, or enrolled nurse at the participating sites in Shinyanga, Tanzania
- Experienced in providing conventional surgical circumcision
- Trained and certified in ShangRing circumcision techniques for the current evaluation by a trainer who is trained in ShangRing application, and has performed a minimum of 10 placements and 5 removals. The evaluation team will bring in ShangRing master trainers from countries with prior ShangRing experience (i.e. Kenya, Zambia) to train providers based in Shinyanga who will then train mid-level providers to conduct ShangRing circumcision, or send physicians from Tanzania to these countries for training.
 - Trained and competent in identifying and managing complications related to ShangRing circumcision.
 - Trained and competent in screening clients to determine their eligibility for ShangRing circumcision.

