Baseline demographics and client characteristics will be presented in tabular format using descriptive statistics. Binary data such as adverse events will be presented as counts and percentages and the upper limit of the estimate of the AE rate (percent of clients with one or more AE) will be based on a two-sided 95% confidence interval. Adverse event rates will be compared descriptively with the reported rates of similar treatments reported in Tanzania and elsewhere, including: comparison against AE rates found in other studies of ShangRing, comparison against AE rates found in studies of other circumcision devices, and comparison against reported rates of AEs in studies of surgical circumcision. No formal hypothesis tests will be done comparing AE rates in this evaluation to other AE rates.

Adverse event rates will be presented by seriousness, severity, relation to device and outcome by site and by cadre. Continuous data will be represented by a mean, standard deviation, median, minimum and maximum together with 95% confidence intervals for the means. The number and percent of subjects who fail to complete the evaluation will be assessed. Time to withdrawal may also be assessed. The procedure time will be calculated. The first 15 procedures performed by each provider will be compared to the last 15 procedures by that provider with respect to procedure time, to evaluate whether procedure time is shortened with experience. All of the first and last 15 procedures evaluated will take place during the main implementation pilot phase. If a provider does not perform 30 total procedures following the training phase, then the first half of the total number of procedures performed will be compared against the last half. Adverse event rates from the training and post-training phases will also be reported, as well as an overall AE rate. Procedure times during the provider training phase will be tracked, but not used for comparisons. The differences in mean procedure times will be compared with a t-test or a non-parametric equivalent.

Standard statistical software packages R, Stata or SAS will be used for the analysis. No corrections for missing values will be imputed. The data will be analyzed and presented “as-is”.

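### Active AE follow-up ends at withdrawal but the man stays in the analysis, so a first AE missed after that point can only lower the primary rate

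*Protocol*

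**What the plan says.** Client Withdrawal Criteria (Protocol) sets the rule for men who withdraw after placement. On retention: "the client will not be replaced and the existing data will be included in the analysis". On further data: "no attempts will be made to collect further data other than that required for clinical documentation of the removal visit". Such a man is not considered for the day 28 interview, "nor will they be asked to return for the day 49 follow-up visit to assess healing". The day 10 call is not named, but it falls under the general stop. He may still come for removal, and he may "contact the clinic should they have further questions, suffer an AE, or experience other difficulties healing". The reason, timing and circumstances of the withdrawal are to be documented and analysed.

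Primary Endpoint (Protocol) sets the window: "The primary endpoint will be assessed at device placement, at device removal, 3-days post removal, at the day 49 post-placement healing assessment". The same sentence goes on to include unscheduled visits within that period.

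Analysis Overview (Protocol) defines the measure and its confidence interval: "the upper limit of the estimate of the AE rate (percent of clients with one or more AE) will be based on a two-sided 95%". On missing data: "No corrections for missing values will be imputed".

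Two other groups with incomplete follow-up have their own rules. Under Procedure for Handling Clients Lost-to-Follow-Up, men who never return for removal are not recorded as having an AE and "also will not be included in calculations when measuring AEs". Under Unscheduled Visits, in the part on calls that clients make because of an AE, a man who phones, does not attend and cannot be traced is scored as a moderate AE by default.

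**The concern.** The primary endpoint is a simple proportion over a fixed window of about seven weeks. A man who withdraws is observed for only part of that window, yet his data stay in the analysis. If he is counted in the denominator and nothing is imputed, his unobserved time is treated as free of AEs. The error has one direction: it can make the device look safer but never less safe.

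The visit that is kept does not close the gap. Appendix XIX lists wound disruption under events during or after removal. In the protocol's own Table 1, wound dehiscence was the most common AE in HIV-negative men (9 of 18 AEs). The protocol does not give the timing of those nine, but this type of event can appear after the last contact that a withdrawn man is asked to keep.

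The AE rate and its upper limit are meant to inform national policy on the device, so a one-directional error in that figure should be either reduced or shown.

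**Working it through.** **The plan's own figure.** Sample Size, Data Collection and Analysis Timeline gives a minimum of 335 men for ±1.5% at a 2% AE rate with 95% confidence. With n = z²p(1−p)/d², z = 1.96, p = 0.02 and d = 0.015, n = 3.8416 × 0.0196 / 0.000225 ≈ 334.6, which rounds up to 335. The figure reproduces. It is not affected by this point.

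**Precision at the full size.** At N = 575 the half-width is 1.96 × √(0.02 × 0.98 / 575) = 0.0114, or 1.14 percentage points. This is the yardstick for any bias.

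**Which men are affected.** The endpoint counts men with at least one AE.
- A man with an AE recorded before withdrawal is already in the numerator. A second, missed AE does not change his status.
- A man with an AE found at the removal visit can be recorded there.
- A man whose first AE comes later and whom nobody sees is scored as AE-free.
- A man whose first AE comes later and who reports it himself may or may not be counted. The text does not say.

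**Bias formula.** Let p be the AE risk in men who stay (2%, from the protocol), w the share withdrawing after placement, r the AE risk of withdrawn men relative to the others, and s the share of withdrawn men with an AE for whom none is captured. The protocol gives no value for w, r or s; all three are assumptions here.

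- True rate = (1−w)p + w·r·p
- Reported rate = (1−w)p + w·r·p·(1−s)
- Shortfall = w·r·p·s

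The upper limits below are rate + 1.96 × √(rate(1−rate)/575), the same normal form as the sample size.

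| w | r | s | True | Reported | Shortfall (points) | Upper limit, true / reported |
|---|---|---|---|---|---|---|
| 1% | 1 | 25% | 2.000% | 1.995% | 0.005 | 3.14% / 3.14% |
| 5% | 1 | 50% | 2.00% | 1.95% | 0.05 | 3.14% / 3.08% |
| 5% | 1 | 100% | 2.00% | 1.90% | 0.10 | 3.14% / 3.02% |
| 5% | 3 | 50% | 2.20% | 2.05% | 0.15 | 3.40% / 3.21% |
| 5% | 3 | 100% | 2.20% | 1.90% | 0.30 | 3.40% / 3.02% |
| 10% | 5 | 50% | 2.80% | 2.30% | 0.50 | 4.15% / 3.53% |
| 10% | 5 | 100% | 2.80% | 1.80% | 1.00 | 4.15% / 2.89% |

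The s = 100% rows are limits, not expectations: they suppose that no AE in a withdrawn man is caught before withdrawal, at removal or by his own report.

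**How the rules meet.** A withdrawn man who never returns for removal is covered both by the rule that keeps his existing data and by the rule that drops him from AE calculations. A withdrawn man who phones about an AE and does not attend is covered both by the rule against seeking further data and by the rule that has him traced and, if not found, scored as a moderate AE. The protocol does not say which rule prevails in either case.

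**The case against.** The strongest reply is that the mechanism is narrow. If men withdraw because of pain or a complication, and that event is recorded, it comes before the withdrawal, is existing data and already counts. This stands, and it limits the bias to first AEs that come after withdrawal.

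Second, stopping attempts to collect data is not the same as refusing to record what presents. Withdrawn men are told to contact the clinic about an AE, the endpoint includes unscheduled visits, and the AE sections require events to be documented, with severe ones reported within 24 hours. A reader might infer that every AE after withdrawal is scored as none. The text does not support that: removal-visit findings are expressly kept, and on self-reported AEs it is silent about counting.

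Third, a reader might infer that withdrawn men and men lost before removal are handled in contradictory ways. Keeping partly observed men and dropping men not seen again after placement is not in itself a contradiction. Only the overlaps need a rule.

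Fourth, that withdrawn men are in the AE denominator is inferred from the retention rule and the definition of the rate. No sentence states it, and denominators are often left to an analysis plan, which is not at hand here. This stands as a caution. It does not settle the matter, because the stop on data collection is fixed in the protocol, and an analysis plan cannot recover data that were never sought.

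**Conclusion.** The point holds in a limited form. Withdrawal ends active AE ascertainment apart from the removal visit, while the man's data remain in an analysis that imputes nothing. On the natural reading of the denominator, a missed first AE after withdrawal lowers the primary rate and its upper limit, and nothing in the rule works the other way.

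The size cannot be known from the protocol. With up to 5% withdrawing and equal risk, the shortfall is at most 0.10 point, small against the 1.14-point half-width. It approaches 1 point, close to the planned precision, only if 10% withdraw, their risk is five-fold and none of their AEs is captured. A large bias is therefore possible under extreme assumptions but is not demonstrated. The case for changing the text is that the direction is known and the remedy is cheap.

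**What to change.** 1. At withdrawal, ask the man's permission to count in the AE rate any AE that he brings to the clinic through day 49, and log refusals. This is one line in the withdrawal procedure and one in the consent form. It asks for no extra visit.
2. State the AE denominator for men who withdraw after placement. Keep those with an AE recorded before withdrawal in both numerator and denominator.
3. Report the planned rate plus two rows for withdrawn men with no recorded AE and incomplete follow-up: one with them removed from the denominator, one with all of them counted as having an AE.
4. Reconcile the withdrawal rule with the exclusion under Procedure for Handling Clients Lost-to-Follow-Up and with the default moderate AE under Unscheduled Visits, and say which applies when a withdrawn man meets more than one.

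The cost is those two lines and two table rows. Men may still refuse, and the worst-case row is wide if withdrawals are common. With 29 of 575 men (5%) withdrawing, none with a recorded AE, and 546 × 0.02 = 10.9 events in the rest, the planned rate is 10.9/575 = 1.9%, the exclusion row 10.9/546 = 2.0%, and the worst case (10.9 + 29)/575 = 6.9%. The exclusion row corrects little if withdrawn men are at higher risk, so it should be read with the worst case and with the reported reasons for withdrawal.

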Client acceptability, time to return to normal activity, and clients' satisfaction with the post-circumcision cosmetic results will be summarized from data recorded on the evaluation surveys and during qualitative interviews conducted with 10% of randomly selected clients. Similarly, provider acceptability will be summarized from data recorded during qualitative interviews conducted with providers. Qualitative interviews will be digitally recorded and then transcribed by qualified staff. The recordings will be transcribed according to the local language used and then to English. The recordings will not be marked with any identifying information but with a unique identifier. Transcriptions will be reviewed electronically, using a qualitative interview analysis software such as Atlas.ti or NVivo, and analyzed for themes. The analysis of the qualitative data will be done through an inductive process where categories are identified as they emerge. Opinions generated by the 10% of clients included in the interviews will be used to tailor the messaging for future program implementation.

The percentage of men healed by day 49, and the time at which all clients are healed, will be reported from data recorded on the client CRFs. The proportion of men unsuitable for ShangRing MC will be extracted from an evaluation log maintained for the purpose of documenting the number of ineligibles and the reasons for their exclusion. Similarly, the number of men who decline ShangRing or who withdrawal will be reported as a proportion.

The photographs taken to document healing and adverse events will be used to supplement the analysis of both endpoints. Photographs will be reviewed only by evaluation project staff, and used to enhance the understanding of different adverse events and as evidence of the duration of the healing process. Photographs of all adverse events (if the client consents) will also accompany the AE reporting, to provide further clarity on these events. The photos will also be used by project staff to better educate ShangRing providers.

Long-Term Data Storage

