Appendix XI – ShangRing Post-Removal Survey

ShangRing Post-Removal Survey

[Table to be completed by Evaluation Staff]

Date (dd/mm/yyyy):	
Client ID:	
Name of Survey Administrator:	
Facility:	

Introduction: Thank you for agreeing to complete this survey to evaluate your experience with the ShangRing circumcision device. This survey asks a few brief questions about your experience with ShangRing now that the device has been removed. Your name will not be recorded anywhere on this survey, and your replies will be kept completely confidential. In this survey there are no right or wrong answers. We are most interested in your honest opinions and reactions to these questions. You may also refuse to answer any question you wish for any reason. The information that you provide will help to determine the future use of ShangRing in Tanzania. If you have any questions about the survey, please do not hesitate to follow up with evaluation staff. If you have difficulty reading or understanding any of the questions, evaluation staff are on hand to read and help you interpret the questions.

1. How much discomfort did you experience while wearing the ShangRing device over the past seven days (circle answer option below)?

I had no discomfort while wearing the ring	I had minor discomfort while wearing the ring	I had moderate discomfort while wearing the ring	I had a lot of discomfort while wearing the ring	Other (comment below)
--	---	--	--	-----------------------

Comment: _____

2. How much did the ring affect you while performing day-to-day activities (circle answer option below)?

It did not affect me at all	It only affected me while performing certain activities	It affected me during all activities, but I could still do them	It prevented me from performing certain activities	Other (comment below)
-----------------------------	---	---	--	-----------------------

Comment: _____

3. After having worn the ring for a week, would you still choose to do ShangRing for circumcision, or would you choose surgery (circle answer option below)?

I would definitely choose ShangRing again	I would probably choose ShangRing again	I would probably choose surgery	I would definitely choose surgery	I don't know
---	---	---------------------------------	-----------------------------------	--------------

Comment: _____

(Survey is continued on next page)

4. How satisfied are you with the appearance of your circumcision (circle answer option below)?

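### The post-removal survey percentages on acceptability will describe only men who were still enrolled and had a removal visit; show them beside a worst-case figure over all men with a device placed.

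*Protocol*

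**What the plan says.** The evaluation goal pairs safety with acceptability. The client acceptability objective gives two examples of what it covers: "need to return to the clinic for device removal, tolerance for leaving device in situ". Client acceptability and satisfaction is a secondary endpoint.

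**When opinions are collected.** Data Collection places one survey after the circumcision on day 0 and a second after device removal at the day 7 visit. The second (Appendix XI) asks about discomfort while wearing the ring, effect on daily activities, satisfaction with appearance and recommending the device. It also asks "After having worn the ring for a week, would you still choose to do ShangRing for circumcision, or would you choose surgery". The day 10 call covers symptoms, the day 49 visit covers healing and adverse events, and the day 28 interview is qualitative and limited to 50 men.

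**What happens on withdrawal.** Client Withdrawal Criteria keeps what a man gave before he left and does not fill his place. From then on, "no attempts will be made to collect further data other than that required for clinical documentation of the removal visit". On the interview, the section says: "The client will subsequently not be included among those selected for the day 28 in-person interview". It also requires a record of why and when he left: "The reason, timing and circumstances of the withdrawal will be documented and analyzed".

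**How it is analysed.** The Analysis Overview states: "No corrections for missing values will be imputed". The data are presented as they stand. For client acceptability it says that "clients' satisfaction with the post-circumcision cosmetic results will be summarized from data recorded on the evaluation surveys", together with the interviews. Withdrawals are reported as a proportion, and the Secondary Endpoints list the number of clients who fail to return as a measure of client acceptability.

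**The concern.** Appendix XI is the only questionnaire that asks every client for his opinion after he has worn the ring. A man who withdraws between placement and removal is not given it, because only the clinical record of his removal is still collected. A man who never comes back has no removal visit at which to answer. With nothing imputed, the denominator of each post-removal percentage becomes the men who answered, and no companion figure over all men with a device placed is planned.

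Whether a man answers may depend on what he would have said, since leaving the evaluation or not returning can itself be a response to the device. When reported acceptance is close to 100%, a handful of absent men can match or exceed the number of recorded unfavourable answers. The results are meant to inform ministry policy, and a reader of the final report could take a respondents-only percentage as the view of everyone who received the ring.

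**Working it through.** **What the protocol lets us reproduce.** Its only precision calculation concerns adverse events: 1.96² × 0.02 × 0.98 / 0.015² = 334.6, rounded up to the stated 335. That figure is correct and is not affected here. The protocol gives no planning figure for acceptability and no expected rate of withdrawal or non-return.

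**Who has a post-removal survey**

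| Client after placement | Post-removal survey? |
|---|---|
| Enrolled, removal visit on day 7 | Yes |
| Enrolled, removal on day 5 or 6 at his request | Yes; the request does not end participation |
| Withdraws after the survey | Yes; existing data are kept |
| Withdraws before removal | No; only clinical documentation of removal |
| Never has a removal visit | No |

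**Inputs for the size**

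- p, the favourable proportion among respondents: 98.7% willing to recommend and 94.6% very satisfied with appearance. Both are figures for HIV-negative men in the cited field study (Introduction, ShangRing and HIV+ Men), used only as illustrations.
- L, the proportion of men with a device placed who have no survey: not given. Assumed 1%, 2% and 5%. Of 575 men these are about 6, 12 and 29.

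**Formulas**

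- Worst case, all absent men unfavourable: p × (1 − L).
- Intermediate, half of them favourable: p × (1 − L) + 0.5 × L.

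| Assumed L | p = 98.7%, worst case | p = 98.7%, half favourable | p = 94.6%, worst case |
|---|---|---|---|
| 1% | 0.987 × 0.99 = 97.7% | 98.2% | 0.946 × 0.99 = 93.7% |
| 2% | 0.987 × 0.98 = 96.7% | 97.7% | 0.946 × 0.98 = 92.7% |
| 5% | 0.987 × 0.95 = 93.8% | 96.3% | 0.946 × 0.95 = 89.9% |

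If the absent men hold the same views as respondents, the figure stays at p, so p is the no-bias case.

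**Two yardsticks**

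- At 98.7%, unfavourable answers number about 0.013 × 575 = 7.5 men. A 2% loss (about 12 men) already exceeds that.
- At about 95% favourable with some 563 respondents (2% loss), the 95% sampling half-width is 1.96 × √(0.95 × 0.05 / 563) = 1.8 points. The worst-case shift at 2% loss is 0.95 × 2 = 1.9 points. From about 2% loss upward, the possible shift is therefore at least as large as the sampling error.

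**The case against.** The strongest reply is that these men are not hidden. Failure to return is a listed measure of client acceptability, withdrawals are reported as a proportion with their reasons, and non-completion is assessed. Clients who miss day 7 get up to five calls, up to four home visits and an offer of removal at an address they gave (Follow-Up Visits), which should keep non-return low. The day 0 survey, which includes a recommendation item, comes before later loss and is retained. Honouring withdrawal and not imputing are legitimate choices in a descriptive single-arm pilot, and survey denominators are often left to a SAP, which is not shown here.

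Most of this stands and limits the point. Three things remain. The separate counts are never joined to the percentages they qualify. The day 0 survey cannot speak to a week of wear. Tracing does not recover answers from men who have withdrawn. As for the SAP, the protocol is not silent: it fixes both the collection rule and the rule that data are presented as they stand.

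A reader might go further and infer that the percentages come only from men who tolerated the ring. The documents do not support that. Any enrolled man who has a removal visit is surveyed, and Appendix XI offers answers for much discomfort, for being prevented from some activities and for definitely choosing surgery. Nor is a request for removal on day 5 or 6 a withdrawal; the protocol says only that it will be granted.

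**Conclusion.** The point holds in a limited form. On the protocol's own rules, the post-removal percentages will be respondents-only, and the absence of the remaining men is plausibly related to their opinion. The direction of any error is therefore likely, but not certainly, upward. A reader might take upward bias as established, but the protocol contains nothing that fixes either its size or its sign. Men may withdraw for any reason, and the section on clients lost to follow-up reports that unremoved rings usually detach on their own, so non-return need not mean dissatisfaction.

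The size depends on the assumed 1% to 5% loss and on counting every absent man as unfavourable. Under those assumptions the fall is about 1 to 5 percentage points, for example from 98.7% to between 97.7% and 93.8%. These are bounds, not predictions. The protocol sets no acceptability threshold that such a shift would cross, and the primary endpoint and sample size are not affected. This is a minor to moderate point on a secondary endpoint, worth acting on because the remedy is cheap.

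**What to change.** In the Analysis Overview, where client acceptability is described, add that:

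- each post-removal percentage is reported with the number of men who had a device placed and the number surveyed;
- beside the respondent figure, a clearly labelled worst-case bound is given over all men with a device placed, counting as non-accepting those who withdrew before the survey and those who never had a removal visit;
- the answers that count as favourable are named for each item, so that the bound is defined;
- the recorded withdrawal reasons are shown alongside;
- both figures are quoted wherever a conclusion on acceptability is drawn.

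The cost is a short paragraph in the protocol and one extra column in the acceptability tables. No further contact with withdrawn men is needed, no clinical procedure changes and no planned analysis is replaced. The drawback is that the bound is conservative, because some men leave for reasons unrelated to the device. It must therefore be labelled as a bound and read together with the reasons.
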